8.3. Variables

8.3.1. Outcome definitions

Primary outcomes/endpoint:

Moderate/severe COPD exacerbations will be identified using an algorithm combining GP visits, prescriptions for oral corticosteroids and/or antibiotics, or hospital admission, as defined using information from study WEUSKOP5893. Rate of exacerbation during the 12 month follow-up will be calculated and compared with the SLS rate in the standard of care arm; if technically possible, exacerbation rates for the 12 months prior to index date (matched enrolment date) would also be compared.

• Pneumonia: To be defined as per the codelist in Table 1 (see 13.1).

Secondary outcomes/endpoints:

- Healthcare utilisation: All GP visits/encounters and all hospital admissions during the 12 month study period.
- Adherence to index prescription: Defined as percent days covered (PDC) and medication possession ratio (MPR) will also be calculated for the matched cohort, as well as discontinuation, switching medicine or adding on other medicines, to be compared with the SLS SOC arm.
- Deaths: All cause, pneumonia death, COPD-attributed death during the 12 month follow-up. For the CPRD, deaths will be determined using Office of National Statistics (ONS) linked mortality data.
- Other definitions of COPD exacerbation: Other definitions will be described as per the outputs of study WEUSKOP5893.

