8.2.1. Inclusion Criteria

Two cohorts will be produced. First, a CPRD cohort, using linked primary care, medication, Hospital Episode Statistics, and socio-economic data, according to the following inclusion criteria:

- 1. Diagnosis of COPD before index date (time period will be defined in the SAP)
- 2. Aged ≥40 at index date.
- 3. Alive, and registered with a GP, at index date.
- 4. Not registered with a GP in the Greater Manchester area.

Second, a Salford cohort will be constructed using the Salford Integrated Record (SIR), according to the inclusion criteria:

- 1. Diagnosis of COPD before index date.
- 2. Aged ≥40 at index date.

WWEpi Project number: PRJ2282

3. Alive, and registered with a GP, at index date.

Restricted cohorts will then be constructed in both the Salford and CPRD populations, based on the inclusion/exclusion criteria and study period for the SLS:

- Patients with documented GP diagnosis of COPD, and currently receiving maintenance therapy
- 2. Male or female subjects aged ≥40 years of age at index date
- 3. Patients who have a history of treatment with systemic/oral corticosteroids, antibiotics (in association with GP contact) and/or hospitalisation for at least one COPD exacerbation in the 3 years prior to index date.
- 4. Current COPD Therapy

All patients currently receiving either:

- inhaled corticosteroid (ICS) alone or in combination with a long acting bronchodilator (this could be a fixed dose combination or an ICS/LABA provided in two separate inhalers, or ICS and LAMA),
- or long-acting bronchodilator therapy alone (e.g. tiotropium or salmeterol, or the use of two bronchodilators i.e. LABA/LAMA),
- or "triple therapy" i.e. ICS/LABA plus a Long Acting Muscarinic Antagonist (LAMA)

Finally, the third data source, the SLS, will be used as-is.

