8.3.3. Confounders and effect modifiers

- Sex
- Age
- Socio-economic status (SES)
- Current/SOC COPD Medication group:

WWEpi Project number: PRJ2282

- LAMA or LABA only
- o LAMA+LABA
- LABA+ICS (combination product or two inhalers)
- o LABA+ICS+LAMA
- Comorbidities
 - Cardio-and cerebrovascular diseases (heart failure, myocardial infarction, stroke)
 - o Depression
 - o Anxiety
 - o Asthma
 - History of pneumonia
 - Gastro-oesophageal reflux and peptic ulcer disease
 - o Diabetes
 - Charlson score (COPD will be removed from score)
- Markers of COPD severity
 - o Previous COPD exacerbation
 - FEV1 % predicted
 - FEV1/FVC ratio
 - GOLD stage
 - MRC Dyspnoea score
- Comedications: major medication classes for each comorbidity of interest
- Smoking
- BMI
- Vaccinations
- Disability status

Further information on the definitions for the variables above will be provided in the SAP.

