Firstly, for descriptive purposes, we will measure the prevalence of the endpoints in a series of subgroups. For example, we will compare the COPD exacerbations in CPRD-xGM-IC with SLS, stratified by SES, gender, etc.

Secondly, we will take a multilevel modelling approach. For this we will combine the SLS and CPRD into one dataset (retaining an indicator of SLS membership). The hierarchies of the model will be patient -> GP practice -> local authority region (with SLS members being treated as a single distinct region) -> strategic health authority region. Strategic health authorities (population threshold of 1 million) are non-anonymised (named) regions. Local authority regions are below the population threshold so an anonymised LA marker will be available.

We will include all confounders and effect modifiers as covariates, with outcomes corresponding to the primary and secondary study outcomes (a separate model for each). Important fixed effects at the local authority level (for example, existence of community teams) will be incorporated into the model if these can be ascertained.

A final model will be selected via backward selection using AIC (Akaike Information Criterion). We will then examine the random effect of the SLS region in the context of the random effects for the other regions. Similar to the above, if the random effect of the SLS region falls outside the 2.5-97.5 percentile range, we will conclude that SOC SLS behaves unusually compared with the rest of the UK, and hence evidence of a Hawthorne effect.

PO3 will be carried out using the same approach as for PO2.

SO1 and SO2 (which pertain to comparing other endpoints, and sensitivity analyses of endpoint definition) will be carried out in the same way as PO2.

SO3 makes explicit the possible change in outcomes at commencement of SLS. We will compare outcome rates within Salford before and after the commencement of SLS, in a self-controlling case design. We will do the same thing within CPRD to control for UK-wide secular trends. This acts as sensitivity analysis to support PO2 (using controls distinct in time rather than in geography).

WWEpi Project number: PRJ2282

Additional work will take place exploring the development of methods for a framework of measuring representativeness; this is not within scope of this protocol and is described in Annex 2.1.

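### The PO2 rule infers a Hawthorne effect from post-index data alone; the pre-index comparison that would help is only conditional, and SO3 does not bind the conclusion

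*Protocol*

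**What the plan says.** The primary outcome is measured after index: "Rate of exacerbation during the 12 month follow-up will be calculated" (Protocol 8.3.1). The same sentence adds the pre-index year as an optional extra: "if technically possible, exacerbation rates for the 12 months prior to index date (matched enrolment date) would also be compared".

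For PO2, 8.7.1 fits a multilevel model in which SLS members form one region, then says: "We will then examine the random effect of the SLS region in the context of the random effects for the other regions". The decision turns on "if the random effect of the SLS region falls outside the 2.5-97.5 percentile range". If it does, the protocol concludes that SLS standard of care is unusual and takes this as evidence of a Hawthorne effect. The pre-index comparison is not mentioned in 8.7.1.

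Three other provisions bear on the point:
- SO3 (8.7.1) compares Salford outcome rates before and after SLS commenced, repeats this in CPRD to control for national time trends, and is described as a sensitivity analysis supporting PO2. It carries no feasibility condition.
- "Previous COPD exacerbation" is a listed severity marker (8.3.3), subject to backward AIC selection (8.7.1).
- Restricted-cohort eligibility requires treatment or "hospitalisation for at least one COPD exacerbation in the 3 years prior to index date" (8.2.1), but "the third data source, the SLS, will be used as-is".

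**The concern.** PO2 exists to tell whether being in the trial changed care and outcomes. A post-index contrast between regions shows only whether SLS differs from elsewhere. A region whose recorded exacerbation rate was always low or high meets the percentile rule as readily as one that changed at trial entry. The protocol itself allows for this: the objective in its research-question section speaks of a Hawthorne effect or other differences, and 8.9 concedes that differences may come from data quality and collection mechanism. The conclusion written into 8.7.1 drops that caution. If it is followed as written, a stable difference would be reported as a Hawthorne effect, and readers would discount the SLS results for the wrong reason.

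**Working it through.** The protocol gives no event rate, power or detectable effect for PO2, so there is no stated figure to reproduce. Every numerical input below that is not attributed to the protocol is an assumption.

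**1. Which contrasts can separate a stable difference from a change**

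| Contrast | Time anchor | Status | Binds the PO2 conclusion? |
|---|---|---|---|
| PO2 random effect (8.7.1) | after index only | co-primary | yes |
| 12 months before index (8.3.1) | each patient's index date | conditional | no |
| SO3 (8.7.1) | commencement of SLS | unconditional, secondary | no |

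The SLS index date is study entry (8.1). For a patient enrolled later, the SO3 period after commencement therefore includes time before that patient's own entry. SO3 also needs Salford data from before the trial without condition, which sits awkwardly with the condition in 8.3.1.

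**2. How often the rule flags a stable offset when the Hawthorne effect is zero**

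Assume normal regional effects, so the limits are ±1.96 between-region SDs; a stable SLS offset *d* and estimation noise *r*, both in SDs; no shrinkage.

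P(flag) = Φ((d − 1.96)/r) + Φ((−d − 1.96)/r)

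| d | r = 0.1 | r = 0.3 | r = 0.5 |
|---|---|---|---|
| 1 | 0.000 | 0.001 | 0.027 |
| 2 | 0.656 | 0.553 | 0.532 |
| 2.5 | 1.000 | 0.964 | 0.860 |

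For example, d = 2.5 and r = 0.5 gives Φ(1.08) = 0.86. Large stable offsets are labelled Hawthorne; modest ones are not.

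**3. What each contrast returns under a stable offset and no Hawthorne effect**

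Simulation with gamma-Poisson counts: 1,400 SOC and 14,000 CPRD patients, mean 1.0 or 1.75 events/year, gamma shape 1 or 2, at least one event in the prior 3 years, 30 replicates per setting.

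| Stable rate ratio | Post-only | Post-only, adjusted for 12-month prior count | Post/pre ratio of rate ratios |
|---|---|---|---|
| 0.8 | 0.82-0.84 | 0.86-0.91 | 0.97-1.00 |
| 1.2 | 1.17-1.18 | 1.07-1.12 | 1.00-1.03 |

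The share of the unadjusted log rate ratio removed by adjustment is 1 − ln(adjusted)/ln(unadjusted). It runs from 1 − ln 0.862/ln 0.825 = 23% to 1 − ln 1.068/ln 1.170 = 58%. A covariate coded as any exacerbation in 3 years would be constant under the eligibility rule and remove nothing.

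The two halves of a post/pre ratio must be adjusted alike. Dividing an adjusted post ratio by an unadjusted pre ratio brings the stable difference back with reversed sign. With a stable ratio of 1.2, mean 1.75 and shape 1, the unadjusted pre ratio is 1.170/1.001 = 1.169, and 1.068/1.169 = 0.91.

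**4. Detectable effects (illustration)**

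Assume 1,400 SOC patients (half the 2,800 target in 8.5), 1.5 events/year, dispersion 0.8, between-region SD τ = 0.10-0.20 on the log scale, within-patient correlation ρ = 0.4-1, region-by-time SD δ, and CPRD sampling error ignored. The detectable reduction at 80% power is 1 − exp(−2.8 × SE).

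- Post-only: SE = √(τ² + (1/1.5 + 0.8)/1400) = 0.105 to 0.203, giving 25% to 43%.
- Post/pre: SE = √(2(1/1.5 + 0.8(1 − ρ))/1400 + δ²).
  - δ = 0: SE 0.031-0.040, giving 8-11%.
  - δ = 0.05: SE 0.059-0.064, giving 15.2-16.5%.
  - δ = 0.08: SE 0.086-0.090, giving 21-22%.

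At τ = 0.10 and δ = 0.08 the comparison is 25% against 21-22%. If drift of 0.08 applies independently in each period, δ² doubles, SE is 0.117-0.120 and the post/pre contrast needs 28-29%, which is worse than post-only at τ = 0.10.

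**The case against.** The strongest reply is that the design already holds the needed contrast. SO3 is a before/after comparison with a CPRD control, planned without condition and named as support for PO2. Previous exacerbation is a candidate covariate, and 8.9 adds a comparison with CPRD data from within Greater Manchester. A reader might infer that the protocol has no means of removing a stable Salford difference. The documents do not support that, because SO3 can do so in substance. What remains is that SO3 is secondary, is anchored on a different date, and cannot alter the PO2 conclusion as written; that the covariate is partial and may be dropped; and that the Greater Manchester comparison addresses data mechanism rather than change at entry.

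A second reply concerns feasibility. A reader might infer that the pre-index rates must be available because eligibility already uses exacerbation history. That does not follow. Eligibility needs one event in 3 years rather than a 12-month rate, SLS data are taken as supplied, 8.7.3 lists comparable variable extraction as a main risk, and the exacerbation code list uses a relaxed definition for comparing CPRD with the Salford EHR on primary care data. The condition in 8.3.1 reflects a documented risk. The code list does show an intention to use a common algorithm, but the look-back of the SLS extract is not stated.

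Third, a before/after contrast can create its own false signal. SLS index dates are real enrolment dates, while CPRD dates are randomly sampled (8.1). If enrolment favours patients with recent events, the SLS pre-index rate is inflated and then falls. A simulation with no Hawthorne effect and no regional difference, in which the recruitment weight rose by an assumed 0.25 per prior-year event (capped at 3), gave a post/pre ratio of 0.91-0.92. That size depends on the assumed weighting, but the point stands and must be disclosed with the fix.

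**Conclusion.** The point holds, centred on the inference in 8.7.1. The post-index regional effect, by itself, cannot distinguish a change at trial entry from a stable Salford or recording difference, yet the protocol reads it as a Hawthorne effect. The pre-index comparison that would help is conditional and has no role in the analysis section, and SO3 does not bind the conclusion.

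The mislabelling matters for large stable offsets: flagging probability is 0.86-1.00 at 2.5 between-region SDs, 0.53-0.66 at 2 SDs, and under 0.03 at 1 SD. In the simulated settings the post/pre ratio returned 0.97-1.03 where post-only returned 0.82-0.84 or 1.17-1.18; this assumes both cohorts are selected alike and regions do not drift. The detectable-effect figures (post-only 25-43%, post/pre 8-22%) illustrate assumed inputs and should not be quoted as properties of this study. The gain is small, or reversed, once regional drift approaches the between-region SD. The wording should be changed before PO2 is analysed; this does not invalidate the design.

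**What to change.** 1. **8.7.1, conclusion.** Say that an outlying SLS effect shows SLS to be unusual. Read it as consistent with a Hawthorne effect only if the before/after contrast against CPRD also shows that SLS changed.
2. **8.3.1, pre-index comparison.** Make the 12-month pre-index comparison of SLS-SOC with CPRD-xGM-IC a planned analysis using the same exacerbation algorithm in both sources. If the SLS look-back proves too short, say so and rest the conclusion on SO3.
3. **Estimate.** Report the post/pre ratio of rate ratios with a 95% CI. Use the same covariate set in both periods, with prior exacerbation left out of both models. Leave out the 2 weeks before index in both sources, because the unstable-COPD exclusion in 8.2.2 makes them event-free (14/365 = 3.8% of the year).
4. **Stated limits.** Name short prior records, possible regional drift, and possible differential regression to the mean from real versus randomly sampled index dates. Check the last by comparing the timing of pre-index events in the two sources. Recording differences cancel only if capture is the same before and after entry.

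The cost is two text changes and one further model run, plus extraction of the pre-index SLS year if it is not already held. SO3 already commits the study to pre-trial Salford data, so the extra burden should be modest, but the protocol does not confirm it.

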6.1. Background

Chronic Obstructive Pulmonary Disease (COPD) is a chronic obstructive disease of the airways associated with a significant social and healthcare burden [1, 2, 3]. Most patients with COPD are managed in primary care, as reflected in recent UK guidelines, which are specifically targeted at primary care physicians [4]. The major goals of treatment are to relieve symptoms, improve activity/exercise tolerance, prevent and treat exacerbations, reduce mortality risk and improve health status. However, despite such guidelines, COPD remains under-diagnosed and under-treated; variations in treatments, standards of care and adherence to guidelines have been reported across different geographical regions [2, 5, 6, 7, 8].

Large computerised patient databases provide a useful source of real life observational data, and the General Practice Research Database (GPRD) has been successfully used to generate descriptive epidemiology data in COPD [9, 10, 11, 12] from a large group of UK primary care practices. Historically, the limitations of the GPRD were a time gap between data capture and availability for the researcher and limited links to other healthcare databases, although these are currently being addressed with the development of the Clinical Practice Research Datalink (CPRD) and in recent Phase 4 pragmatic clinical trials [12]. The use of electronic medical record (EMR) data in health research is a key objective in the Department of Health's national research strategy [13].

The Salford Lung Study (SLS) is an ongoing Ph IIIB pragmatic trial comparing a new once daily ICS/LABA fixed dose combination (RELVAR: fluticasone furorate + vilanterol) in which patients are identified by EMR, enrolled in their GP office, randomized to RELVAR or Standard of Care (SOC) maintenance therapy and followed for safety and effectiveness via linked primary care/secondary routine care with primary endpoint of COPD moderate/severe exacerbations over 12 months [14]. MHRA and NICE provided joint advice for the SLS protocol and were supportive of the design to generate "real world" evidence which will demonstrate the value and safety of the medicine against the most relevant standard of care.

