SO1: To make comparisons between the SLS Standard of Care and the CPRD cohort on the following health care utilisation (HCU) endpoints: GP visits, hospital admissions mortality and adherence.

SO2: To evaluate other definitions of COPD exacerbation in SOC from CPRD.

SO3: Self-controlled comparison of COPD and other HCU endpoints in Salford before and after SLS commenced.

WWEpi Project number: PRJ2282

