8. RESEARCH METHODS

8.1. Study Design

This will be an observational COPD cohort study that will utilize the CPRD and the Salford EHR system – to compare selected cohorts with SLS.

For SLS, reference/index date is study entry. This will be matched in CPRD by the following algorithm:

1. Draw up a long-list of potentially eligible individuals in CPRD (patients who would be eligible at some point during the SLS recruitment phase).

2. For each individual:

- a. Randomly sample an entry date from full list of SLS entry dates.
- b. If patient is eligible at that entry date, then they will be included, accounting for relevant immortal time biases up to that entry date, otherwise, they will be excluded. Further details on methods of reducing immortal time bias (i.e left truncated at the entry date and survival modelling) will be outlined in the SAP.

First, the COPD populations in both Salford and in the wider CPRD (excluding Greater Manchester area) will be compared. Second, we will focus on comparisons between all patients enrolled in the SLS SOC arm versus a CPRD cohort that would have been eligible for SLS as per the inclusion and exclusion criteria.

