8.6.3. Timings of Assessment during follow-up

As per SLS protocol for SLS patients. CPRD and SIR patients are observational only.

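### The GP-visit endpoint does not separate trial-driven contacts from routine care, so an SLS excess in SO1 or SO3 could be misread as a Hawthorne effect

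*Protocol*

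**What the plan says.** **Endpoint.** Protocol Section 8.3.1 lists healthcare utilisation among the secondary outcomes: "All GP visits/encounters and all hospital admissions during the 12 month study period". It names no exclusion and does not say whether the index day counts. It does not defer this definition to the SAP, although other sections defer particular items explicitly.

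**Comparison.** The purpose of SO1 is "To make comparisons between the SLS Standard of Care and the CPRD cohort on the following health care utilisation (HCU) endpoints"; GP visits come first in that list. SO3 compares healthcare use in Salford before and after the trial started.

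**Who has study contacts.** Section 8.6.3 on timing of assessments reads: "As per SLS protocol for SLS patients. CPRD and SIR patients are observational only". Section 6.1 says that SLS "patients are identified by EMR, enrolled in their GP office" and are then "followed for safety and effectiveness via linked primary care/secondary routine care".

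**Index date.** Under Section 8.1 the SLS index date is study entry. For each CPRD candidate the instruction is: "Randomly sample an entry date from full list of SLS entry dates". The draw requires no contact with the practice on that date.

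**Data handling.** Section 8.2.1 on cohort construction ends: "Finally, the third data source, the SLS, will be used as-is".

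**Decision rule.** Section 8.7.1 examines the SLS region's random effect for PO2. If it lies outside the 2.5 to 97.5 percentile range of the regional effects, that is taken as evidence of a Hawthorne effect. SO1 is to be analysed by the same method.

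**The concern.** Section 6.2 describes the Hawthorne effect of interest as a change in how GPs and nurses behave and decide while the trial is running. A contact that happens because the trial requires it is not such a change, yet the endpoint counts it in the same way as a visit the patient or GP chose. Only SLS patients can have such contacts. If they enter the practice record, they push the SLS region towards the upper tail that Section 8.7.1 reads as a Hawthorne effect.

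No planned step removes them:

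- The covariates in Section 8.3.3 cannot adjust for something that occurs only in SLS.
- The comparison with CPRD patients in Greater Manchester (Section 8.9) uses people who also have no trial contacts.
- The CPRD secular-trend control in SO3 contains no trial contacts either, so it cannot subtract those in Salford's after period. Section 8.7.1 presents SO3 as support for PO2.

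The protocol already applies the principle elsewhere. The exacerbation code list in Annex 2 discards candidate events recorded on the day of a formal COPD review. The GP-visit count has no comparable rule.

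**Working it through.** The protocol gives no GP-visit rate, no number of SLS contacts and no between-region variance, so there is no planned figure to reproduce. What follows is illustration on stated assumptions.

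**Inputs, all assumed**

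- b, background GP encounters per patient-year: 6, 12 or 20.
- k, trial contacts recorded as GP encounters per patient-year: 1. Enrolment is the only practice contact the text supports.
- s, between-region standard deviation of the log rate: 0.10, 0.20 or 0.30.

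**Step 1: apparent rate ratio with no true difference.** If trial contacts add to routine ones, RR = (b + k)/b = 1 + k/b.

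- b = 20: 21/20 = 1.05
- b = 12: 13/12 = 1.08
- b = 6: 7/6 = 1.17

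**Step 2: chance that the decision rule flags SLS with no true effect.** Ignoring shrinkage and sampling error,

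P = 1 − Φ(1.96 − ln RR/s) + Φ(−1.96 − ln RR/s).

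For k = 0 this is 5%. For k = 1, b = 12, s = 0.10: ln(13/12)/0.10 = 0.80, so P = 1 − Φ(1.16) + Φ(−2.76) = 12.6%.

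| k = 1 | s = 0.10 | s = 0.20 | s = 0.30 |
|---|---|---|---|
| b = 6 | 33.8% | 12.0% | 8.1% |
| b = 12 | 12.6% | 6.9% | 5.8% |
| b = 20 | 7.8% | 5.7% | 5.3% |

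**Step 3: contacts needed to reach the 97.5th percentile with no true effect.** k* = b(exp(1.96s) − 1), over s = 0.10 to 0.30:

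- b = 6: 1.3 to 4.8 a year
- b = 12: 2.6 to 9.6 a year
- b = 20: 4.3 to 16.0 a year

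On these assumptions one contact raises the false-flag chance but does not by itself carry SLS to the threshold. Several recorded contacts could. The protocol does not say how many there are.

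**The case against.** A reader might infer that the trial's scheduled contacts do count as GP visits in SLS, and that the protocol therefore creates the difference it would call a Hawthorne effect. The protocol does not support that. It gives neither the number nor the place of follow-up assessments and does not say they are coded as GP encounters. Section 6.1 points the other way, since follow-up runs through linked routine records. Even the enrolment contact is counted only if the index day is included and the contact is recorded as an encounter, and the text settles neither.

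Three further objections carry weight:

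- **Additivity.** A study contact may replace a routine review. If a share r of contacts does so, RR = 1 + k(1 − r)/b, which falls to 1 when r = 1.
- **SAP detail.** What counts as an encounter is often settled in the SAP, and Section 8.7.3 lists matching of outcome definitions across sources as a risk. Section 8.9 also concedes that differences may come from how data were collected. But its examples are diagnoses, pneumonia and pharmacy data, and an SAP that dropped trial contacts would depart from the endpoint as Section 8.3.1 words it.
- **One-sided deletion.** Removing contacts from SLS alone could remove routine care that CPRD patients keep, biasing SLS downwards and hiding a real increase. This objection shapes the fix.

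**Conclusion.** The point holds conditionally. The endpoint wording does not separate trial-driven from routine GP contacts. Only SLS patients can have the former, and the decision rule would attribute a resulting excess to changed behaviour. The protocol states this rule, so it is more than detail left for later.

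The size cannot be determined from the protocol. For one additive contact the artefact is a rate ratio of 1.05 to 1.17, with a false-flag chance of about 5% to 34% against a nominal 5%. This rests on the assumed b of 20 to 6 and s of 0.10 to 0.30. The artefact could be nil if trial contacts are not coded as encounters or replace routine ones, and larger if several are recorded.

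The scope is narrow: the GP-visit component of SO1 and SO3. The point does not by itself show bias in the other SO1 endpoints (hospital admissions, mortality and adherence), and nothing here concerns the primary objectives directly. It is worth correcting before analysis, but it does not threaten the study as a whole.

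**What to change.** 1. In Section 8.3.1, count GP visits/encounters from the day after the index date, in both cohorts. Entry dates are already needed for the Section 8.1 algorithm, so this requires no new data. If CPRD contacts are spread evenly over the year, the rule drops on average b/365 of a contact there: 6/365 = 0.02 to 20/365 = 0.05.
2. For SO1 and SO3, report GP-visit counts with and without SLS protocol-scheduled contacts, where these can be identified in the SLS data.
3. In Section 8.7.1, state that an SLS excess in GP visits is read as a Hawthorne effect only if it remains when trial contacts are excluded. If they cannot be identified, that condition cannot be checked and the excess should be reported descriptively.

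The cost is a few sentences and one extra count. The protocol does not show that SLS visit dates or visit types reach the analysts, and Section 9.2 says the data are anonymised before transfer, so availability needs to be confirmed with the SLS team. The downside is that routine care delivered at a study contact is lost from the restricted count, which is why both counts should be shown.

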8.9. Limitations of the research methods

Hawthorne effect can only be evaluated for the SOC comparison. This does not give definite evidence about whether the prognostic or predictive effect of RELVAR would differ in the general population. This information could only truly be obtained following use of RELVAR in the general population.

There is no direct metric by which 'representativeness' of the Salford cohort can be measured. Early explorations of this will be made in a companion project – see Annex 2.1.

WWEpi Project number: PRJ2282

While both the SLS and CPRD use GP data, some data (hospital validated COPD diagnoses, pneumonia data, pharmacy data) for participants in SLS are collected using a different mechanism to CPRD. In this study protocol, only serious pneumonia defined by hospitalization will be assessed, which is a subset of total pneumonia cases recorded in the SLS. Hence any differences (either in representativeness or treatment response) observed between the SLS and non-SLS cohorts could be attributed to differences in data quality and the data collection mechanism. This will be mitigated by an additional comparison of SLS data with CPRD data from within Greater Manchester.

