Annex 2: Code lists for key definitions using in study PRJ2282/201491

- 1. Medical codes considered to identify those with COPD in the CPRD
- 2. Code lists for moderate/severe COPD exacerbation used in CPRD and SLS-EHR
- 3. Code list to define Hospitalised pneumonia (PO3 and SO2) in CPRD

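### SO1 applies the Hawthorne outlier rule to adherence, although SLS pharmacy data come from a different collection mechanism and the stated mitigation cannot separate source from region

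*Protocol*

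**What the plan says.** The objectives (abstract, and the list after 6.2) make adherence one of the SO1 contrasts between SLS standard of care and CPRD: "GP visits, hospital admissions mortality and adherence".

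Section 8.3.1 gives the measures: "percent days covered (PDC) and medication possession ratio (MPR) will also be calculated for the matched cohort". The same entry covers three kinds of treatment change in CPRD patients and names the SLS standard-of-care arm as the comparator for all of these measures.

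Section 8.7.1 carries out SO1 in the same way as PO2. SLS and CPRD are pooled in a multilevel model in which SLS members form a single region. If the SLS regional effect lies outside the 2.5 to 97.5 percentile range, the plan concludes that SLS is unusual and takes this as evidence of a Hawthorne effect.

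Section 8.9 lists hospital-validated diagnoses, pneumonia data and pharmacy data as collected differently: "pharmacy data) for participants in SLS are collected using a different mechanism to CPRD". It accepts that differences between the cohorts "could be attributed to differences in data quality and the data collection mechanism", and adds: "This will be mitigated by an additional comparison of SLS data with CPRD data from within Greater Manchester". Section 8.7.3 names as a main risk whether outcomes can be extracted from both datasets with the same or similar definitions.

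**The concern.** PDC, MPR, discontinuation, switching and add-on are all computed from records of medicine supply. Among the SO1 endpoints they are therefore the most exposed to a difference in pharmacy data. If the SLS values come from pharmacy supply and the CPRD values from prescriptions issued in general practice, one endpoint name covers two quantities: medicine obtained and medicine prescribed.

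What is at stake is the reading of the result. The rule in 8.7.1 has one interpretation for an outlying SLS region, namely Hawthorne. A source difference could produce such a finding with no change in behaviour, or could offset a real change and hide it. The protocol discloses the limitation, but the remedy it attaches does not address it, and the decision rule takes no account of it.

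**Working it through.** The plan states no figure for adherence, so there is nothing to reproduce. The check is whether the planned comparisons can separate source from behaviour.

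**1. Identification.** Let b be the true adherence difference for SLS patients after adjustment, and s the offset due to the SLS data mechanism. Every SLS patient carries both and no CPRD patient carries either. The model estimates only the sum:

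SLS regional effect = b + s

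For any constant c, the pair (b + c, s − c) fits the data equally well. No patient, practice or area covariate changes this, because none varies with source inside SLS or inside CPRD.

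**2. The stated mitigation.** Let g be the Greater Manchester difference, and b′ what remains of b once geography is removed.

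| Comparison | What it contains |
|---|---|
| SLS v CPRD outside Greater Manchester | g + b′ + s |
| SLS v CPRD-GM (8.9) | b′ + s |
| CPRD-GM v CPRD-xGM (8.7.1) | g |

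The mitigation removes g and leaves s in place, because CPRD-GM is collected as the rest of CPRD is. It is also absent from the comparisons listed in 8.7.1, and that list is written for PO1.

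**3. Contrast with exacerbations.** The code-list annex includes "Code lists for moderate/severe COPD exacerbation used in CPRD and SLS-EHR". Its section 2 relaxes event type (1) for comparisons of CPRD with the Salford EHR on primary care data alone. The protocol thus shows a common primary-care definition being applied to Salford records. It states nothing equivalent for adherence.

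**4. How the rule responds to an offset (illustration only).** Assume normal regional effects with known limits, no true difference, and a source offset of d between-region standard deviations. Then

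P(flag) = P(|Z + d| > 1.96) = Φ(−1.96 + d) + Φ(−1.96 − d)

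| d | 0 | 0.5 | 1 | 1.5 | 2 | 3 |
|---|---|---|---|---|---|---|
| P(flag) | 5.0% | 7.9% | 17.0% | 32.3% | 51.6% | 85.1% |

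The same formula shows masking. A true difference of 2 SD is flagged 51.6% of the time; with an opposite source offset of 2 SD the net shift is 0 and the probability falls to 5.0%. The documents give no value for d, so the table shows how the rule behaves and does not estimate the bias.

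**The case against.** The strongest reply is that the protocol never says SLS adherence will be built from pharmacy supply. Section 8.3.1 speaks of adherence to the index prescription, 8.1 says the study uses the Salford EHR system, 8.4 says the SIR holds prescriptions, and the annex applies CPRD-style code lists to SLS-EHR data. A prescription-based SLS measure fits this text, and the record source and PDC algorithm commonly belong in the SAP. The risk is also disclosed twice, in 8.7.3 and 8.9. All of this stands, and it limits the point to a possible bias. It does not rescue the mitigation, which the protocol does state and which cannot work, nor the rule that reads an outlier as Hawthorne.

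Other safeguards can be cited. SO3 compares endpoints in Salford before and after SLS began, and a constant source offset would cancel where one source covers both periods. SIR v CPRD-GM is planned to expose data-quality differences. Section 8.3.2 adds Salford COPD patients outside SLS as a third group. But SO3 is a separate analysis offered in support of PO2, SIR v CPRD-GM is listed for PO1 characteristics and not for PDC or MPR, and nothing ties the third group to the adherence question. None alters the SO1 adherence contrast as written.

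Two stronger readings are tempting. A reader might take "Finally, the third data source, the SLS, will be used as-is" to mean that SLS endpoints enter without harmonisation. That sentence closes the inclusion criteria in 8.2.1 and most naturally concerns who is in the SLS population. A reader might also infer that SLS adherence will look lower, because uncollected prescriptions count only in CPRD. That holds only if SLS uses dispensing data, which the protocol does not say.

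**Conclusion.** The point holds in conditional form. The SO1 adherence contrast confounds region with data source, the stated mitigation leaves that confounding untouched, and the Hawthorne rule is applied regardless. If SLS adherence rests on pharmacy supply, an outlying SLS effect could be due to the source.

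Neither size nor direction can be derived from the documents. It would be tempting to assume a rate of uncollected prescriptions and express the resulting PDC shift in standard errors of a two-group difference. The inputs would all be outside the documents, and the yardstick would be wrong: 8.7.1 judges SLS against the spread of regional effects. Adherence is one component of one secondary objective and is not an outcome in PO1 to PO3, so the weight is moderate. The case for change is that the remedy is cheap and the protocol itself admits the source difference.

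**What to change.** 1. State in 8.3.1 which records supply the SLS adherence measures.
2. Derive PDC, MPR, discontinuation, switching and add-on in both cohorts from GP-issued prescriptions: CPRD on one side, the Salford/SLS EHR prescribing records on the other, with one common days-supply rule. That rule needs attention, because the relaxed exacerbation definition in the annex drops the 5 to 14 day duration condition without giving a reason; comparability of recorded duration should be checked first.
3. Report any pharmacy-based SLS PDC descriptively, for SLS only.
4. If a common source is not feasible, do not apply the Hawthorne rule to adherence, and say so in 8.7.1.
5. In 8.9, do not present the Greater Manchester comparison as mitigating the source difference for adherence.

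The cost is some programming, and more if days' supply must be imputed. The statistical downside is that prescription-based PDC overstates actual use, but it does so in both cohorts.
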